--	--

[Type here]

[Type here]

[Type here]

	
unresected primary tumors or local tumor recurrence following resection are not eligible
 
10. Female patients of childbearing potential must have a negative pregnancy test (urine), must not be breastfeeding and using adequate contraceptive measures.
 
Female patients must use a highly effective contraceptive measure from screening until 4 months after the last dose of drug. All methods of contraception (except for total abstinence) should be used in combination with the use of a condom by a male sexual partner for intercourse (see Restrictions below). (or vasectomy)
 
Female patients must have evidence of non-childbearing potential by fulfilling one of the following criteria at screening:
 
a. Post-menopausal women defined as aged more than 50 years and amenorrhoeic for at least 12 months following cessation of all exogenous hormonal treatment.
 
b. Documentation of irreversible surgical sterilisation by hysterectomy, bilateral oophorectomy, or bilateral salpingectomy, but not tubal ligation.
 
11-1. For the duration of the study and for 1 week after the last study drug administration, sexually active male patients must be willing to use barrier contraception i.e. condoms with all sexual partners. Where the sexual partner is a 'women of child-bearing potential' who is not using effective contraception, men must use a condom (with spermicide) during the study and for 6 months after the last dose of a study drug. (or vasectomy)
 
12. Mandatory biopsy during the screening window prior to dosing and at progression (if clinically feasible)
 
Exclusion Criteria
 
Patients who meet any of the following criteria will be excluded from participation in this study:
 
 1. The patient has documented and/or symptomatic, encephalitis, brain or leptomeningeal metastases. 2. The patient has experienced any Grade 3 to 4 GI bleeding within 3 months prior to enrollment. 3. The patient has experienced myocardial infarction, transient ischemic attack, cerebrovascular accident, or unstable angina, within 6 months prior to enrollment. 4. The patient has a history of deep vein thrombosis (DVT), pulmonary embolism (PE), or any other significant thromboembolism (venous port or catheter thrombosis or superficial venous thrombosis are not considered "significant") during the 3 months prior to first dose of protocol therapy. 5. Has received a live vaccine within 30 days prior to the first dose of study drug. Examples of live vaccines include, but are not limited to, the following: measles, mumps, rubella, varicella/zoster (chicken pox), yellow fever, rabies, Bacillus Calmette–Guérin

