 - ✓ Total bilirubin $\leq 1.5 \times$ institutional upper limit of normal (ULN)
 - ✓ AST (SGOT)/ALT (SGPT) $\leq 3.0 \times$ institutional upper limit of normal unless liver metastases are present in which case it must be $\leq 5 \times$ ULN
 - ✓ Serum creatinine $\leq 1.5 \times$ institutional ULN
 - ✓ Glomerular filtration rate < 45 mL/min in assessed by standard methods in the laboratory
 - ✓ urinary protein is $\leq 1+$ on dipstick or routine urinalysis
 - ✓ (INR) ≤ 1.5 and (PTT) \leq x5 seconds above the ULN (unless receiving anticoagulation therapy). Patients on anticoagulation therapy with unresected primary tumors or local tumor recurrence following resection are not eligible.

[Type here]

[Type here]

[Type here]

11. Female patients of childbearing potential must have a negative pregnancy test (urine or serum), must not be breastfeeding and using adequate contraceptive measures.

Female patients must use a highly effective contraceptive measure from screening until 4 months after the last dose of drug. All methods of contraception (except for total abstinence) should be used in combination with the use of a condom by a male sexual partner for intercourse (see Restrictions below). (or vasectomy)

Female patients must have evidence of non-childbearing potential by fulfilling one of the following criteria at screening:

- a. Post-menopausal women defined as aged more than 50 years and amenorrhoeic for at least 12 months following cessation of all exogenous hormonal treatment.
- b. Documentation of irreversible surgical sterilisation by hysterectomy, bilateral oophorectomy, or bilateral salpingectomy, but not tubal ligation.

11-1. For the duration of the study and for 1 week after the last study drug administration, sexually active male patients must be willing to use barrier contraception i.e. condoms with all sexual partners. Where the sexual partner is a 'women of child-bearing potential' who is not using effective contraception, men must use a condom (with spermicide) during the study and for 6 months after the last dose of a study drug. (or vasectomy)

12. Biopsy during the screening window prior to dosing and at before cycle 3 (if clinically feasible)

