7.2 Enrollment/screening Period

The following assessments and procedures should be performed within 28 days prior to first dose of study treatment. For details of the schedule and nature of the assessments, see below.

- Signed informed consent for the study; include main inform consent
- Results of EBV IHC or PDL1 (EBV positive or PDL1 CPS≥5)

EBV test: (all centralized at CAP-certified pathology lab/SMC): he entire procedure was performed on a fully automatic system (BOND-MAX) for in situ hybridization with an EBV-encoded RNA probe from Leica (Newcastle, UK) following manufacturer's instructions (ref: Gastroenterology [Type here] [Type here] [Type here])

Pembrolizumab + Ramucirumab (Ver 2.5, Oct 2024)
2010 vol 139, pages 84-92).

PDL1 test: IHC staining will be carried out on Dako Autostainer Link 48 system (Agilent Technologies, Santa Clara, CA) using Dako PD-L1 IHC 22C3 pharmDx kit (Agilent Technologies) with EnVision FLEX visualization system and counterstained with hematoxylin according to the manufacturer's instructions. PD-L1 protein expression will be determined by using Combined Positive Score (CPS), which was the number of PD-L1 staining cells (tumor cells, lymphocytes, macrophages) divided by the total number of viable tumor cells, multiplied by 100. (ref: https://www.agilent.com/cs/library/usermanuals/public/29158_pd-l1-ihc-22C3-pharmdx-nslcl-interpretation-manual.pdf)

- Date of birth, race and ethnicity
- Medical and surgical history
- Current and concomitant medications including previous cancer therapies (if applicable)
- Physical examination
- ECOG performance status
- Vital signs (blood pressure, pulse and body temperature), body weight and height.
- Hematology, clinical chemistry and urinalysis, TFT
- Menopausal status; serum or urine pregnancy test for women of childbearing potential (within 7 days prior to study treatment start
- ECG
- Echocardiogram/MUGA Should be completed if patients had received prior anthracycline therapy
- Tumor assessment (scans of the abdomen/pelvis/other sites as clinically indicated for assessment of disease [CT/MRI]), performed within 14 days prior to enrollment, ideally should be performed as close as possible to the start of the treatment. Scans that were performed as part of standard of care prior to signature of the informed consent form can be analysed for the purposes of the study if they were performed within the correct time frame and consistent with modified RECIST guidelines for CT or MRI

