14.1 Laboratory Parameters

All laboratory tests will be performed at local labs and should be done to ensure patients meet all eligibility criteria and criteria to continue on the protocol:

Hematology Profile – Includes a complete blood count with differential and platelet count.

[Type here]

[Type here]

[Type here]

Pembrolizumab + Ramucirumab (Ver 2.5, Oct 2024)

Coagulation Profile – Includes INR, prothrombin time, and PTT.

Chemistry Profile – Includes creatinine, AST, ALT, alkaline phosphatase, total protein, and bilirubin.

NOTE: If pretreatment serum creatinine is >1.5 times the ULN, calculate creatinine clearance

Urinalysis – Includes routine UA or dipstick measurements and, if clinically indicated, microscopic analysis

Serum -HCG Pregnancy Test – Minimum sensitivity 25 IU/L or equivalent units of β -HCG, to be performed within 28 days prior to enrollment for WOCBP.

TFT Test - T3, FT4 and TSH

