 - b. Treatment cycle defined herein as 6 weeks; however, there will be no treatment interruption or break between cycles. Patients will continue to undergo treatment according to program protocol until there is evidence of disease progression, toxicity requiring cessation, withdrawal of consent, or until other withdrawal criteria are met.
 - c. End of therapy evaluations will be performed at the discontinuation of therapy; patients should be followed for at least 30 days after last dose of protocol therapy to ensure sufficient safety monitoring and any AEs reported unless another therapy has been commenced and the AE is thought related to post-program therapy. Written informed consent must be obtained prior to any program-specific pretreatment evaluations and before patient enrollment.
 - d. WOCBP must have a negative serum pregnancy test within 7 days prior to enrollment.
 - e. To be obtained within 28 days prior to enrollment only for patients with prior anthracycline therapy. Subsequent evaluations are not required, but may be done at the discretion of the patient's physician if warranted by dyspnea or other relevant symptoms.
 - f. Baseline imaging to determine the extent of disease and identify metastases, and tumor assessments should be performed within 14 days prior to enrollment, and every 6 weeks (± 3 days) until documented progression for patients with disease status of complete response (CR), partial response (PR), or stable disease (SD), and/or for patients who have discontinued program therapy due to toxicity or reasons other than progressive disease.
 - g. Including temperature, pulse rate, respiration rate, and blood pressure; to be obtained before, during, and at the completion of each infusion.
 - h. In situations where hemoglobin is less than 9 g/dL (5.58 mmol/L) and there are signs or symptoms of bleeding, a hematology profile should be performed weekly until hemoglobin is ≥ 9 g/dL (5.58 mmol/L) and any bleeding-related signs or symptoms have resolved or been adequately investigated.
 - i. Every 6 weeks or in accordance with local regulations, whichever is of shorter duration.
 - j. All SAEs considered at least possibly related to ramucirumab and pembrolizumab will be followed until resolution, stabilization, return to baseline, or until deemed irreversible.

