The patient has experienced any arterial thromboembolic events, including but not limited to myocardial infarction, transient ischemic attack, cerebrovascular accident, or unstable angina, within 6 months prior to first dose of protocol therapy.

The patient has uncontrolled or poorly-controlled hypertension (> 160 mmHg systolic or > 100 mmHg diastolic for > 4 weeks) despite standard medical management.

Discontinuation of a patient from a ramucirumab clinical trial:

Patients with grade 4 hypertension must not receive further treatment with Ramucirumab.

Reproductive Precautions

To be included in a ramucirumab clinical trial:

[Type here]

[Type here]

[Type here]

Pembrolizumab + Ramucirumab (Ver 2.5, Oct 2024)

Because the teratogenicity of ramucirumab is not known, the patient, if sexually active, must be postmenopausal, surgically sterile, or using effective contraception (hormonal or barrier methods). Female patients of childbearing potential must have a negative serum pregnancy test within 7 days prior to first dose of protocol therapy.

To be excluded from a ramucirumab clinical trial:

The patient is pregnant or breast-feeding.

The patients with lung cancer (NSCLC and SCLC) regardless of tumor histology should be excluded from a ramucirumab clinical trial:

If they experience hemoptysis (defined as bright red blood or $\geq 1/2$ teaspoon) within 2 months prior to first dose of protocol therapy or with radiographic evidence of intratumor cavitation or has radiologically documented evidence of major blood vessel invasion or encasement by cancer.

General Medical Disorders

Discontinuation of a patient from a ramucirumab clinical trial:

Patients with grade 3 or 4 infusion-related reactions must not receive further treatment with ramucirumab.

Ramucirumab should be permanently discontinued in the event of a gastrointestinal perforation or fistula formation.

If Reversible Posterior Leukoencephalopathy (RPLS) is diagnosed, ramucirumab must be permanently discontinued. All cases of RPLS must be reported via the SAE mechanism.

Prior Medical History Precautions

To be excluded from a ramucirumab clinical trial:

The patient has a prior history of GI perforation/fistula (within 6 months of first dose of protocol therapy) or risk factors for perforation.

The patient has a serious or nonhealing wound, ulcer, or bone fracture within 28 days prior to first dose of protocol therapy.

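### The inclusion item on childbearing potential contradicts itself, and the specimen and timing of the pregnancy test differ between sections

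*Combined protocol and SAP*

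**What the plan says.** **Who may enrol.** Section 6.1 opens by requiring every patient to meet each criterion, and Section 6.3 says that the enrollment criteria are to be followed explicitly. Item 11 begins: "Female patients of childbearing potential must have a negative pregnancy test (urine or serum), must not be breastfeeding and using adequate contraceptive measures". Its second paragraph requires contraception of female patients from screening until 4 months after the last dose. Its third paragraph reads: "Female patients must have evidence of non-childbearing potential by fulfilling one of the following criteria at screening". The two qualifying conditions are being over 50 and amenorrhoeic for at least 12 months, or documented irreversible surgical sterilisation. Item 10 of the synopsis has the same structure and the same third paragraph.

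**Which test, and when.**
- Synopsis, item 10: "Female patients of childbearing potential must have a negative pregnancy test (urine", with no window.
- Section 6.1, item 11: urine or serum, with no window.
- Section 7.2: "serum or urine pregnancy test for women of childbearing potential (within 7 days prior to study treatment start".
- Section 14.1: a serum test, "to be performed within 28 days prior to enrollment for WOCBP".
- Appendix 1, footnote d: "WOCBP must have a negative serum pregnancy test within 7 days prior to enrollment".
- Appendix 2, Reproductive Precautions: "Female patients of childbearing potential must have a negative serum pregnancy test within 7 days prior to first dose of protocol therapy".

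Appendix 2 opens by saying that its items must be carried into the eligibility and discontinuation sections. On this topic it treats menopause, surgical sterility and effective contraception as alternatives, and says that the teratogenicity of ramucirumab is unknown.

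**The concern.** An eligibility item should give one answer for any given patient. For a premenopausal woman who has not been sterilised, item 11 gives two: the first paragraph lets her in and the third shuts her out. For the test that supports the first route, the answer depends on which section the site opens.

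Two different things are at stake, and they belong to different readings. If the third paragraph binds, women for whom the rest of the protocol makes provision are kept out. If it does not bind, fertile women are dosed on the strength of a single screening test whose validity rules conflict. The Appendix 1 schedule marks that test in the screening column only, with nothing on Cycle 1 Day 1. Pregnancy is an exclusion criterion, but before dosing that exclusion depends largely on this test.

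**Working it through.** No statistical figure is involved, so the check sets the texts side by side and counts days.

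**Step 1: can one woman satisfy the whole of item 11?** Paragraph one applies to women of childbearing potential. Paragraph three applies to female patients without restriction and requires evidence of the opposite status. No 'or' or conditional joins them. A fertile woman satisfies paragraph one and fails paragraph three. A postmenopausal or sterilised woman satisfies paragraph three and does not need paragraph one. Read literally, paragraph one therefore admits nobody.

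**Step 2: what does the rest of the protocol assume?** Sections 7.2 and 14.1, Appendix 1 footnote d and Appendix 2 all set a pregnancy test for women of childbearing potential. Section 10.2.2 asks for pregnancies during maternal exposure to be reported. Appendix 2 offers contraception as an alternative to menopause or sterility. These provisions fit a trial that enrols fertile women, but none of them amends item 11.

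**Step 3: the test rules side by side.**

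| Place | Specimen | Window | Anchor |
|---|---|---|---|
| Synopsis, item 10 | urine | none | none |
| 6.1, item 11 | urine or serum | none | none |
| 7.2 | serum or urine | 7 days | treatment start |
| 14.1 | serum | 28 days | enrollment |
| Appendix 1, footnote d | serum | 7 days | enrollment |
| Appendix 2 | serum | 7 days | first dose |

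That is three specimen rules and, where a window is given, three timing rules.

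**Step 4: four illustrative tests** (the days are chosen for illustration).
- Urine, 5 days before enrollment and dosing on the same day: meets the synopsis, 6.1 and 7.2; fails 14.1 and both appendices.
- Serum, 20 days before enrollment: meets 6.1 and 14.1; fails 7.2 and both appendices.
- Serum, 6 days before enrollment, with dosing 3 days later: 6 + 3 = 9 days before dose. Meets 14.1 and Appendix 1; fails 7.2 and Appendix 2, because 9 > 7.
- Serum, 5 days before enrollment and dosing on the same day: meets 6.1, 7.2, 14.1 and both appendices. Only the urine wording in the synopsis is not met.

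**Step 5: the longest test-to-dose interval.** The introduction to 7.2 places all screening procedures within 28 days before first dose, and the Appendix 1 screening column runs from day -28 to day -1. Appendix 1 footnote a anchors screening to enrollment instead, so the cap is not stated uniformly. Taking the 7.2 limit, a site that relies on 14.1 alone could dose on a test up to about 28 days old. Under 7.2 or Appendix 2 the limit is 7 days. The difference is 28 - 7 = 21 days.

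**The case against.** The strongest reply is that these are drafting slips which a sensible site would resolve. An 'or' was probably dropped from item 11, and Appendix 2 shows the intended structure. The windows are nested: a serum test within 7 days of both enrollment and first dose meets every text except the synopsis specimen. The 28-day figure stands once, in a general laboratory section, against three statements of 7 days. To use it, a site would have to disregard the screening section, the schedule footnote and Appendix 2.

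Much of this stands. It makes a long test-to-dose interval unlikely and limits the practical harm. It does not remove the contradiction in item 11, because the current text contains no 'or' and Section 6.3 requires the criteria to be followed as written.

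A reader might infer that Section 14.1 allows an interval of at least 28 days with no upper limit. The documents do not support that. A window is a maximum, and 7.2 and the Appendix 1 column cap screening at 28 days before dosing. A reader might also infer that a pregnancy conceived in the interval meets no safeguard at all. Item 11 requires highly effective contraception from screening, used with a condom, and pregnancy is a separate exclusion. These lower the risk, although contraception does not detect a pregnancy.

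**Conclusion.** The point holds as an internal inconsistency in the operative eligibility text, present in both criteria lists, together with conflicting rules for the only scheduled pre-dose pregnancy test. The consequence for test age is conditional. It needs fertile women to be admitted and a site to rely on Section 14.1 alone, and then the test could be up to about 28 days old at dosing instead of 7.

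Wrongful exclusion and an outdated test cannot both happen to the same woman, since each belongs to a different reading of item 11. The documents also do not settle whether fertile women are meant to be enrolled. The testing and contraception provisions and Appendix 2 suggest it, but the stated objective refers only to patients with metastatic gastric or GEJ adenocarcinoma.

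The share of women affected is not given. The primary endpoint, sample size and error rates do not depend on this point. It should be corrected because it bears on eligibility and safety and is cheap to fix.

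**What to change.** Reconcile six places: synopsis item 10, Section 6.1 item 11, Section 7.2, Section 14.1, Appendix 1 footnote d (with its schedule row) and Appendix 2. They should state one rule on whether women of childbearing potential may enrol, and if so one specimen, one window and one anchor (enrollment or first dose). The sponsor should make each choice and check it against the Appendix 2 text, which the protocol itself says must appear in the criteria. At present neither criteria list gives a window, and neither requires the specimen that Appendix 2 names. If fertile women are to be eligible, item 11 must show explicitly how its first and third paragraphs relate.

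The cost is an amendment to wording and, depending on the choice made, a change in test timing for some patients. Nothing in the sample size or the analysis needs to change.

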6.2 Exclusion Criteria

Patients who meet any of the following criteria will be excluded from participation in this study:

1. The patient has documented and/or symptomatic encephalitis, brain or leptomeningeal metastases.
2. The patient has experienced any Grade 3 to 4 GI bleeding within 3 months prior to enrollment.
3. The patient has experienced myocardial infarction, transient ischemic attack, cerebrovascular accident, or unstable angina, within 6 months prior to enrollment.
4. The patient has a history of deep vein thrombosis (DVT), pulmonary embolism (PE), or any other significant thromboembolism (venous port or catheter thrombosis or superficial venous thrombosis are not considered "significant") during the 3 months prior to first dose of protocol therapy.
5. Has received a live vaccine within 30 days prior to the first dose of study drug. Examples of live vaccines include, but are not limited to, the following: measles, mumps, rubella, varicella/zoster (chicken pox), yellow fever, rabies, Bacillus Calmette–Guérin (BCG), and typhoid vaccine. Seasonal influenza vaccines for injection are generally killed virus vaccines and are allowed; however, intranasal

[Type here]

[Type here]

[Type here]

Pembrolizumab + Ramucirumab (Ver 2.5, Oct 2024)

influenza vaccines (eg, FluMist®) are live attenuated vaccines and are not allowed

6. The patient has an ongoing or active infection, symptomatic congestive heart failure, unstable angina pectoris, symptomatic or poorly controlled cardiac arrhythmia, uncontrolled thrombotic or hemorrhagic disorder, or any other serious uncontrolled medical disorders in the opinion of the treating physician.
7. The patient has ongoing or active psychiatric illness or social situation that would limit compliance with treatment.
8. The patient has uncontrolled or poorly controlled hypertension (>160 mmHg systolic or >100 mmHg diastolic for >4 weeks) despite standard medical management.
9. The patient has a serious or nonhealing wound, ulcer, or bone fracture within 28 days prior to enrollment.
10. The patient has received chemotherapy, radiotherapy, immunotherapy, or targeted therapy for gastric cancer within 2 weeks prior to enrollment.
11. The patient has received any investigational therapy within 30 days prior to enrollment.
12. The patient has undergone major surgery within 28 days prior to enrollment, or subcutaneous venous access device placement within 7 days prior to enrollment.
13. The patient has received prior therapy with an agent that directly inhibits VEGF (including bevacizumab), or VEGF Receptor 2 activity, or any antiangiogenic agent and immunotherapy.
14. The patient is receiving chronic antiplatelet therapy, including aspirin, nonsteroidal anti-inflammatory drugs (NSAIDs; including ibuprofen, naproxen, and others), dipyridamole or clopidogrel, or similar agents. Once-daily aspirin use (maximum dose 325 mg/day) is permitted.
15. The patient has a known allergy to any of the treatment components.
16. Has had a prior anti-cancer monoclonal antibody (mAb) within 4 weeks prior to study Day 1 or who has not recovered (i.e., \leq Grade 1 or at baseline) from adverse events due to agents administered more than 4 weeks earlier.
17. Has active autoimmune disease that has required systemic treatment in the past 2 years (i.e. with use of disease modifying agents, corticosteroids or immunosuppressive drugs). Replacement therapy (eg., thyroxine, insulin, or physiologic corticosteroid replacement therapy for adrenal or pituitary insufficiency, etc.) is not considered a form of systemic treatment.
18. Has a history of (non-infectious) pneumonitis that required steroids or has current pneumonitis.
19. Has an active infection requiring systemic therapy.
20. Has a known history of Human Immunodeficiency Virus (HIV) (HIV 1/2 antibodies).
21. Has known active Hepatitis B or Hepatitis C (e.g., HCV RNA [qualitative] is detected) and liver cirrhosis. Chronic HBV infection with anti-viral agent prophylaxis is allowed.
22. Has known liver cirrhosis at a level of Child-Pugh B (or worse) or cirrhosis (any degree) and a history of hepatic encephalopathy or clinically meaningful ascites resulting from cirrhosis. Clinically meaningful ascites is defined as ascites from cirrhosis requiring diuretics or paracentesis.
23. The patient is pregnant or breastfeeding.

